9. INTERVENTIONS

There will be no intervention to the standard of care these patients receive. However, consented participants will be asked to make two study visits where a multiparametric MRI scan will be performed – these visits will be defined as visit 2 and visit 3. An optional echocardiogram may be included at Visit 2. The example guidelines provided in Appendix 1 should be taken into consideration when imaging research participants to ensure the safety of both staff and participants, whilst helping to further prevent the spread of COVID-19.

10. DATA

10.1. Data Collection and Management

All MRI imaging data will be pseudonymised before being uploaded to the custom-built data management system at Perspectum Ltd. No other parties will be able to access identifiable information (with the exception of the study team who will upload the data).

Relevant medical history and demographics will be extracted from the patients' medical notes by a local study investigator and subsequently entered into an eCRF. The blood and urine samples will be processed at the local clinical site laboratory and the results entered into the eCRF by the local study team.

All paper documents containing personal data (e.g. informed consent forms) will be stored securely and only accessible by local study staff and authorised personnel. The study investigator is responsible for keeping these documents in a secure and accessible format to ensure that, in case of an emergency, patients can be identified and contacted. The

enrolment log that links a participant’s study ID to their personal information will be kept for 5 years after study completion or until ethical approval terminates, whichever is sooner (please refer to section 11).

All study data will be stored for a minimum of five years after the end of the study in line with GCP recommendations.

10.2. Analysis plan

Descriptive statistics will be used to summarise subject characteristics. Summary data will be calculated for MRI metric values (Table 3). Normality will be determined by use of the Shapiro-Wilk test. Results will be expressed as means with standard deviation (SD) for continuous variables and as numbers and percentages for categorical variables.

Analysis of variance will be used to test for differences between multiple groups.

The primary endpoint will be a comparison of MRI metric values for fibro-inflammation in the liver compared to a matched non-diabetic control group from the UK Biobank(30) or from other studies (31) (Table 3). This will be assessed with a two-sample, two-sided t-test. Secondary endpoints include a comparison of individual MRI metric values [summarised in table 3 below] in individual organ associated with T2D and its comorbidities [summarised in table 3 below] at baseline (visit 1/visit 2) compared to a matched non-diabetic control group from the UK Biobank or other studies. These will also be assessed with two sample, two-sided t-tests. Additionally, the prevalence of mean liver PDFF and / or mean liver cT1 above NAFLD thresholds in the study cohort will be compared to the matched non-diabetic control group, using a Chi-squared test.

MRI metric	Organ(s) or Location(s)	Associated organ characteristic
For primary endpoint		
cT1	Liver	Fibro-Inflammation
For secondary endpoints		
Diameter of Aorta	Heart	Local Blood Flow
Aortic Distensibility	Heart	Elasticity of Aorta
T1	Spleen, Kidney, Pancreas	Fibro-Inflammation
T2*	Spleen	Iron Level
PDFF	Liver, Spleen, Pancreas	Fat content
Volume	Liver, Spleen, Kidney, Pancreas	Size
Optional exploratory endpoint metrics		
T2* Gradient	Kidney	Oxygenation
D	Kidney	Glomerular Filtration
PDFF	Kidney	Fat Content

Volume of Visceral Adipose Tissue (VAT)	Abdomen	Fat Content
Abdominal Subcutaneous Adipose Tissue Volume (ASAT)	Abdomen	Fat Content
Skeletal Muscle Index	Abdomen	Muscle Content

Table 3 - MRI metrics in relevant organs

Change from baseline in MRI metrics values at 6 to 9-months post-treatment will be assessed as secondary endpoints in each organ. These will be assessed with linear mixed effects model with an interaction variable of time. The change from baseline in proportion of patients at 6 to 9 months with mean PDFF and / or mean cT1 above NAFLD thresholds, across the whole study cohort, will be assessed using Chi-squared tests. Equivalent changes from baseline at 6 to 9 months will be assessed for HbA1c (glycaemic control), and other circulating biomarkers utilised in the clinical pathway for T2D, NASH and CKD [serum creatinine and eGFR (kidney), urine albumin creatinine ratio (kidney), lipids (NALFD), LFT (liver)], using linear mixed effects to assess changes over time. Odds ratios will be calculated by logistic regression analysis in relation to cardiovascular, liver, pancreatic and kidney-related events and or death, including hospital admissions, at 1, 3 and 5 years from baseline.

Exploratory endpoints will investigate the potential influence of glycaemic control/weight and of glucose/lowering therapies (oral/injectable agents) on prevalence of abnormality based on thresholds set from the healthy controls and on rate of progression for both biochemical and MRI-metrics, in subgroup analyses (including subgroups with abnormalities in multiple organs). Multiple testing will be corrected with Bonferroni correction. In addition, analysis of covariance will provide estimates of MRI metrics, adjusting for potential confounders such as baseline MRI metric, type of co-morbidity, type of therapeutic, HbA1c values, anthropometric measures and organ-specific circulating biomarker values as covariates. Similarly, additional associations of MRI metrics to biomarkers that are optional [for example left ventricular strain from the ECHO] or not in standard of care [for example pancreatic lipase] may be analysed, if evaluated locally or from stored, consented additional blood samples. Thresholds will be set based on Kaplan–Meier analysis to establish the proportions of patients in different MRI metric categories that remain free of diabetes-related events in the follow-up period. Differences between the curves will be compared using the log-rank test.

The results will be expressed as effect sizes and 95% confidence intervals (95% CI). Spearman and/or Pearson’s correlations will be calculated to test associations between categorical and / or continuous variables, for example significant correlations between MRI metrics and weight, and between MRI metrics and biochemical metrics. To determine the diagnostic utility of MRI in these cohorts for assessing organ dysfunction, receiver-operating characteristic analyses will be carried out.

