To address this growing need, we propose adding a complementary imaging aspect to the currently used biomarkers. MRI, specifically, provides excellent soft-tissue contrast. Perspectum’s LiverMultiScan™ is a quantitative multiparametric MRI method, FDA-cleared and CE-marked, that is used to detect and stage early liver disease. It is already widely used in pharmaceutical trials for NAFLD therapeutics. The MRI metrics from LiverMultiScan™ can quantify changes to liver tissue characteristics, like fibro-inflammation and fat, as a result of intervention (for example, bariatric surgery - see Fig. 1). The accuracy and reproducibility of LiverMultiScan™ has been demonstrated in studies scanning patients within different MRI scanners. It continues to be further supported by data from clinical trials in liver disease cohorts, from comparative studies that include healthy controls, as well as whole-population studies in the UK and US (17–24).

[figure not shown]

Figure 1 - Example of MRI metrics and images from LiverMultiScan™ before and after bariatric surgery

With this study we aim to develop a new MRI image analysis technique, “ATLAS”, that builds on LiverMultiScan™ technology. We also plan to gather clinical evidence that will demonstrate the potential added value to the NHS, as well as support future regulatory clearance. The phenotypical information that ATLAS delivers, combined with information from circulating biomarkers, will form the basis of a future clinical decision support tool for T2D (Fig. 2).

[figure not shown]

Figure 2 – An example schematic of the impact of ATLAS in the clinical pathway of T2D, based on MRI metrics of liver and cardiovascular system health

Perspectum has pilot data showing that LiverMultiScan can:

- estimate portal hypertension (spleen),
- detect pancreatitis,
- characterise the tissue of the kidneys

This study looks at the potential to extend LiverMultiScan to each of the other relevant organs – pancreas, kidneys and spleen. The technical development of “ATLAS” will be complemented by the accumulation and analysis of clinical data, circulating biomarkers and imaging. This information will be obtained from three diverse UK clinical centres (Liverpool, Oxford and London).

The innovation comes from combining a number of quantitative MRI metrics to achieve this (Fig. 3):

- volumes - for liver, spleen, kidneys, pancreas (25–27);
- fibroinflammation: cT1 and/or T1 – for liver, spleen, kidneys, pancreas (25);

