Visit 1 - Baseline, Day 0	0 weeks	
 ● Medical Hx ● Blood Tests ● Basic measurements (incl. height, weight, BMI, hip & waist circumference) ● Urine Sample ● Questionnaire
Visit 2	Within 35-days of Visit 1	
 ● MRI Scan ● BP (optional) ● ECHO (optional) ● Questionnaire
Visit 3	6-9 months	
 ● Medical Hx ● Blood Tests ● Basic measurements (incl. height, weight, BMI, BP) ● Urine Sample ● Questionnaire

Visit	Time	Visit Details
		
 ● MRI ● Medical Record Review

Further to this, participants will be asked to give consent to the review of their medical records at 3 time points - years 1, 3, and 5, following baseline assessment. This review will be conducted by authorised study investigators who will obtain clinical outcome measures relating to the study objectives, for example, measures of liver or kidney function.

In the majority of cases, follow-up data at years 1,3,5 will be entered from participants’ medical records. However, some participants may receive a short telephone call at years 1,3,5 to clarify any data which may be unclear or, to supply data which may be missing from their medical record. All participants recruited and scanned at Perspectum Ltd. in Oxford (a non-NHS clinical study site) will complete their years 1,3,5 follow-up medical history over the telephone: although all participants have consented to a medical records review during the study, medical records are not available to staff outwith the NHS. Thus self-reported data will be collected from these participants.

[figure not shown]

Figure 4 - Schematic of patient recruitment and study pathway (participants will be asked to confirm an absence of COVID-19 symptoms prior to each visit and may undergo a temperature measurement if necessary)

b. Study Setting

This is a multi-centre study conducted in 4 localities:

- 1) Liverpool
- 2) Oxford (Oxford University Hospitals NHS Foundation Trust - OUHNHSFT)

- 3) London (in the catchment of the Royal Free NHS Foundation Trust)
- 4) Oxford (Perspectum Ltd.)

Site 1) and 2) to recruit 50 T2D patients each, with the remaining 50 patients to be recruited between sites 3) and 4). Recruitment will be carried out from various settings to include community, primary care and secondary care diabetes clinics. Imaging will be carried out at local imaging centres for each locality.

5. Study Participants

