5.2. Exclusion Criteria

- The participant may not enter the study if they have any contraindication to magnetic resonance imaging (standard MR exclusion criteria including pregnancy, extensive tattoos, pacemaker, shrapnel injury, severe claustrophobia).
- Patients with known autoimmune hepatitis, viral hepatitis, Wilson's disease, haemoglobinopathies or significant structural renal tract abnormality.
- Patients with known excessive alcohol intake.
- Any other cause, including a significant disease or disorder which, in the opinion of the investigator, may either put the participant at risk because of participation in the study, or may influence the participant's ability to participate in the study.

6. Sample size

The primary endpoint of the study is to compare the MRI metrics for liver fibroinflammation in those patients with type 2 diabetes at baseline vs. individuals who are healthy and non-diabetic. Values for the healthy, non-diabetics will be provided from data from the UK Biobank (UKBB)(30) or from other studies (31). Healthy individuals will be matched to the diabetic population based on gender, age and ethnicity. Analysis will be based on a two-sample, two-sided t-test.

The sample size required to perform a t-test with 90% power and alpha of 0.05 would require n=150. Based on MRI metric for liver fibroinflammation (cT1) this assumes:

- Detection of a 24.87 ms difference in cT1 in liver (This represents 50% of the difference in cT1 between self-reported diabetes vs healthy subgroups within the UK Biobank), based on unpublished data from Perspectum)
- SD of 42ms (pooled SD from self-reported diabetes and healthy subgroups within UKBB, based on unpublished data from Perspectum)
- 20% drop-out rate.

Secondary endpoints of the study include separate comparisons of MRI metrics for liver fat infiltration and volume in patients with type 2 diabetes vs. the same metrics in healthy, non-diabetic individuals. Values for the healthy, non-

diabetics will be provided from data from the UK Biobank (30) or or from other studies (31) and will be selected based on the matching of gender, age, ethnicity to the patients from this study with type 2 diabetes. Analysis will be based on two-sample, two-sided t-tests.

Based on MRI metric for liver fat infiltration (PDFF), the sample size required to perform the t-test with 90% power and alpha of 0.05 would require n=150. This assumes:

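### Baseline T1 (and spleen T2*) comparisons use external controls not matched on MRI acquisition, so any scanner or sequence difference would be confounded with diabetes

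*Protocol*

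**What the plan says.** **Metric.** Table 3 in Protocol Section 10.2 assigns "cT1 Liver Fibro-Inflammation" to the primary endpoint. Under the secondary endpoints it lists "T1 Spleen, Kidney, Pancreas Fibro-Inflammation", and T2* for spleen. Section 2.1 is less definite and gives "fibroinflammation: cT1 and/or T1 – for liver, spleen, kidneys, pancreas".

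**Patients.** Section 4b states: "Imaging will be carried out at local imaging centres for each locality". Section 7.3.1 puts all participants through one standardised ATLAS imaging protocol. It names no scanner model or field strength.

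**Controls.** Under Section 10.2 the secondary metrics are "compared to a matched non-diabetic control group from the UK Biobank or other studies". Section 6 gives the selection rule: "Healthy individuals will be matched to the diabetic population based on gender, age and ethnicity". Field strength, sequence and scanner are not in it.

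**Test.** Section 10.2 says of the secondary baseline comparisons: "These will also be assessed with two sample, two-sided t-tests". The exploratory analysis of covariance has an open-ended list of confounders, and scanner, site and data source are not among those named.

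**Cross-scanner evidence.** Section 2.1 states: "The accuracy and reproducibility of LiverMultiScan™ has been demonstrated in studies scanning patients within different MRI scanners". That sentence concerns the liver product. The same section presents pancreas, kidneys and spleen as organs to which the study may extend it.

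**The concern.** In this design, data source and disease group coincide. The protocol recruits only patients with type 2 diabetes for scanning at its centres, and every control value is imported. If the two sets of images were acquired differently in a way that shifts T1 or T2*, the shift adds directly to the estimated diabetes difference. Matching on gender, age and ethnicity does not remove it, and the t-test has no term for it.

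For the liver, the protocol offers some protection in its statement on reproducibility across scanners. It offers none for T1 in the other three organs or for spleen T2*.

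The organ comparisons of secondary outcome 2 are at stake. A positive result could be technical in whole or in part, and an offset of opposite sign could hide a real difference. The exploratory prevalence of abnormality in Section 10.2 uses thresholds derived from the healthy controls, so those thresholds would move by the same offset.

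**Working it through.** **1. The plan's own figure.** The nearest stated figure is the Section 6 sample size for liver cT1: difference 24.87 ms, SD 42 ms, two-sided alpha 0.05, power 90%, 20% drop-out.

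- n per group = 2 × (1.960 + 1.282)² × 42² / 24.87² = 59.9, rounded up to 60.
- Total = 2 × 60 = 120. After drop-out, 120 / 0.8 = 150.

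The stated 150 reproduces as the total of two equal groups, so this point is not about a wrong number. Section 6 gives no effect, SD or sample size for T1 in spleen, kidney or pancreas, or for spleen T2*.

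**2. What the planned comparison estimates.** Let δ be the true diabetes difference and b the mean acquisition offset between patient and control scans. The expected difference in group means is δ + b. This is one equation with two unknowns. A scanner covariate can separate them only if some patients and some controls share equipment or acquisition, which nothing in the protocol requires.

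**3. Size under an assumed offset.** The documents give no offset, so b is an assumption, expressed in SD units of whichever metric is tested. Other inputs:

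- Patients: Section 4b recruits 150; with 20% loss, 150 × 0.8 = 120 evaluable.
- Controls: no ratio is stated. I take 1:1 (120) and, as a second assumption, 5:1 (600).
- δ = 0; two-sided 5% t-test.

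The non-centrality is b / √(1/n₁ + 1/n₂):

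- 120 vs 120: √(1/120 + 1/120) = 0.129, so it is 7.75 × b.
- 120 vs 600: √(1/120 + 1/600) = 0.100, so it is 10 × b.

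Rejection probabilities from the non-central t distribution:

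| Assumed offset b (SD) | 120 vs 120 | 120 vs 600 |
|---|---|---|
| 0 | 5% | 5% |
| 0.1 | 12% | 17% |
| 0.2 | 34% | 52% |
| 0.3 | 64% | 85% |
| 0.5 | 97% | over 99% |

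Hand check at b = 0.2, 120 vs 120: the non-centrality is 1.55 and the critical value 1.97. P(Z > 0.42) is about 0.34, which agrees.

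Adding controls makes the error worse, because it narrows the standard error around δ + b and not around δ.

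**4. What is not touched.** The change from baseline at 6–9 months (Section 10.2, linear mixed effects model) is within patients and uses no external control.

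**The case against.** The strongest reply is that the documents do not show any scanner difference. They name no scanner or field strength for patients or for controls. Controls from other studies might share equipment or acquisition with a study site, and the sponsor is itself a site. This stands: a difference is a risk and not a documented fact. A reader might infer that the T1 comparisons are already confounded, or that no control was scanned on compatible equipment. The protocol supports neither reading. What remains is that the selection rule does not require acquisitions to coincide.

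Second, no passage says that T1 or T2* varies with field strength or sequence, or what the correction in cT1 removes. That also stands. The argument needs only that acquisition can shift these metrics. The protocol itself treats agreement across scanners as something to be demonstrated, and cites the demonstration for the liver product only.

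Third, patients share the ATLAS protocol, and Section 2.1 leaves cT1 open for all four organs. The common protocol helps comparability among patients but says nothing about how controls were imaged. The cT1 wording conflicts with Table 3, which is the operative list for the analysis.

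Fourth, acquisition detail may sit in an analysis plan or imaging manual that is not shown. It may, and naming demographic factors does not forbid further restriction. However, the protocol itself states the matching factors and the unadjusted test. A manual for patient scans also cannot change how existing control scans were made; only control selection can act on that.

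A reader might also gauge the offset in milliseconds against the 42 ms SD in Section 6. That SD is for liver cT1 and does not carry over to T1 in other organs.

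**Conclusion.** The point holds conditionally. For T1 in spleen, kidney and pancreas, and T2* in spleen, the stated matching rule and test leave any acquisition difference between patients and controls confounded with diabetes, and the protocol gives no cross-scanner assurance for these metrics.

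Its size cannot be derived from the documents. Under the assumptions shown (120 vs 120, no true effect), the false-positive rate runs from 5% with no offset to about 97% at 0.5 SD, and is about 34% at 0.2 SD. If field strength and sequence already coincide, the offset is near zero and results are unchanged.

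The effect is confined to secondary baseline comparisons and the exploratory thresholds taken from the controls. This point does not challenge the primary liver cT1 comparison. A reader might extend it to the 6–9 month change, but that analysis does not use these controls and no defect is shown there. Because the remedy is a better selection rule at low cost, the change is worth making even though the risk is unquantified.

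**What to change.** - In Sections 6 and 10.2, state the scanner and field strength for patients and for each control source. For the T1 and T2* comparisons, match or restrict controls on field strength and on T1/T2* sequence, in addition to gender, age and ethnicity.
- Process patient and control scans for these metrics with the same software version.
- Where no compatible controls exist for an organ, report its baseline comparison descriptively, without a test against controls.
- Reconcile Section 2.1, which leaves cT1 or T1 open for these organs, with Table 3, which fixes T1.

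The cost is protocol wording and selecting controls from acquisition metadata. The downside is a smaller eligible control pool for these metrics and possibly no formal test for some organs.

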3. STUDY OBJECTIVES

The main objective of this study is to assess the health of multiple organs over a period of 6 to 9 months, using multiparametric abdominal MRI, in patients with type 2 diabetes who have been prescribed glucose lowering therapy (as per their standard of care).

Primary Objective	Primary Outcome Measure
1. To determine the degree of liver fibroinflammation in a large cohort of patients with type 2 diabetes, using multi-parametric abdominal MRI.	MRI metrics for liver fibroinflammation in patients with type 2 diabetes vs. the same metrics in healthy, non-diabetic individuals at baseline.
Secondary Objectives	Secondary Outcome Measures
1. To determine the degree of other liver abnormalities (such as fat infiltration) in a large cohort of patients with type 2 diabetes, using multi-parametric abdominal MRI.	1. Liver MRI metrics in patients with type 2 diabetes vs. the same metrics in healthy, non-diabetic individuals, at baseline for: 
 fat infiltration organ volume proportion of patients with evidence of non-alcoholic fatty liver disease (based on thresholds for liver fat or fibroinflammation).
2. To determine the degree of abnormality in other organs associated with type 2 diabetes and its	2. MRI metrics in patients in patients with type 2 diabetes vs. those in healthy, non-diabetic individuals, at baseline for:

comorbidities (pancreas, spleen, kidneys, aorta) using multi-parametric abdominal MRI
	
 organ volume, fat infiltration and fibroinflammation in abdominal organs affected by type 2 diabetes (spleen, pancreas, kidney) aortic health (aortic distensibility, diameter).

3. To assess whether multi-parametric abdominal MRI can quantify changes in multiple organs (liver, kidneys, pancreas, spleen and aorta) that occur over 6-9 months.
	
3. At 6-9 months: difference from baseline across the cohort in the following MRI metrics:
 
 organ volume, fat infiltration and fibroinflammation in abdominal organs affected by type 2 diabetes (liver, spleen, pancreas, kidney) aortic health (aortic distensibility, diameter) proportion of patients with evidence of non-alcoholic fatty liver disease (based on thresholds for liver fat or fibroinflammation).

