4. STUDY DESIGN

a. Study Description

This will be a multi-site study adopting a prospective, observational, longitudinal, cohort study design. There will be no intervention to the standard of care. Participants will be required to attend a screening visit and additional study visits on up to three time points – baseline (visit 1), a visit within 35 days of baseline (visit 2) and at 6-9 months (visit 3). The second and third visit will involve having a multiparametric MRI scan. Where possible some visits (the screening visit 1 or visit 1 /visit 2) may be on the same day or within standard of care, depending on patient and MRI scanner availability. The screening visit may be able to take place remotely over the phone, depending on the preference of the participant and the study team, facilitated by the use of an online platform to obtain Informed Consent. In consideration of the COVID-19 pandemic, prior to each study visit, participants will be asked to confirm whether they have experienced any

of the documented symptoms. Participants may also undergo a temperature measurement at the discretion of the local clinical care team.

Patients with type 2 diabetes and prescribed with glucose lowering therapy (as per standard of care) will be recruited from community settings, primary care centres and diabetes clinics within secondary care settings (see Fig. 3). We aim to recruit patients who have been newly prescribed medication; also, those patients undergoing treatment intensification (when an additional treatment is being considered due to evidence of poor glycaemic control), as per their standard of care HbA1c level results. Clinical outcome measurements, blood samples and urine samples will be collected to assess the response to standard of care treatment. There will be an optional thoracic echocardiogram (ECHO) included at visit 2. This is a non-invasive way in which we can capture data to enable us to assess cardiovascular disease.

Study participants will be enrolled in this study for a total of 5-years. During this time, consented participants will be asked to attend for up to 3 study visits: Visit 1 (baseline), Visit 2 and Visit 3.

Visit	Time	Visit Details
Screening visit	0 weeks	
 ● Informed Consent ● Medical Record Review

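### The change in the proportion above NAFLD thresholds is measured twice in the same patients, but Section 10.2 names only chi-squared tests and no paired form

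*Protocol*

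**What the plan says.** Secondary outcome 3 in Protocol Section 3 is defined within one cohort: "At 6-9 months: difference from baseline across the cohort in the following MRI metrics". One of its components is the proportion of patients with evidence of NAFLD, based on thresholds for liver fat or fibroinflammation.

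Section 10.2 gives the analysis. The shift over this interval in the share of patients whose liver readings lie "above NAFLD thresholds, across the whole study cohort, will be assessed using Chi-squared tests".

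Three other places bear on how to read this:

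- **Design.** Section 4 says "The second and third visit will involve having a multiparametric MRI scan". Section 9 repeats that "consented participants will be asked to make two study visits where a multiparametric MRI scan will be performed", and Table 1 in Section 7.3 marks MRI at Visits 2 and 3. Each completing patient therefore supplies both a baseline and a follow-up reading.
- **Same test name, different design.** Earlier in Section 10.2 the prevalence above the thresholds "in the study cohort will be compared to the matched non-diabetic control group, using a Chi-squared test". That comparison is between two groups of different people.
- **Continuous changes.** For the continuous MRI metrics over the same interval: "These will be assessed with linear mixed effects model with an interaction variable of time". The biomarkers also get linear mixed effects models.

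**The concern.** The ordinary Pearson chi-squared test compares two independent samples. Here each patient contributes to both proportions, and a patient above a threshold at baseline is likely still to be above it 6-9 months later. The test has no term for that correlation. When the correlation is positive, its standard error is too large, real change is harder to detect, and an interval built the same way is wider than it need be. Section 10.2 promises effect sizes with 95% CIs, so the interval matters as well as the p-value.

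A second literal reading is possible: a chi-squared test on the cross-table of baseline status by follow-up status. That tests whether the two readings are associated, not whether the proportion changed. It would usually be significant when nothing had changed, and could be misread as evidence of change.

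This is not a detail left for a later document. The protocol does name a test for this endpoint, and on its natural reading that test does not match the design.

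**Working it through.** The protocol gives no power, sample size or expected effect for this endpoint, so there is no stated figure to reproduce. What follows illustrates the cost of the test choice.

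**Inputs**

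- Pairs: 120 = 150 × (1 − 0.20). Both figures come from Section 6, where the 20% drop-out is stated for the t-test sample sizes.
- Baseline proportion: 60%, the literature prevalence of NAFLD in type 2 diabetes in Section 2.1. It is not the prevalence above this study's thresholds.
- Fall to 50%: assumed.
- Within-patient correlation φ: assumed, shown over a range.
- Two-sided 5% level, no continuity correction.

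**Paired model.** Probability above the threshold at both visits: p11 = p1·p2 + φ·√(p1·q1·p2·q2). With p1 = 0.6 and p2 = 0.5 the square root is √(0.24 × 0.25) = 0.245. Down and up cells of 25% and 15%, for example, give p11 = 0.35 and φ = (0.35 − 0.30)/0.245 = 0.20.

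**Power for a fall from 60% to 50%, 120 pairs** (at least 200,000 simulated cohorts per row)

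| φ | Down / up | Pearson | McNemar | Exact McNemar |
|---|---|---|---|---|
| 0 | 30% / 20% | 34% | 34% | 30% |
| 0.20 | 25% / 15% | 32% | 41% | 36% |
| 0.41 | 20% / 10% | 29% | 52% | 45% |
| 0.61 | 15% / 5% | 25% | 72% | 63% |

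**95% CI half-width**

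- Unpaired: 1.96 × √((0.24 + 0.25)/120) = 12.5 points.
- Paired: 1.96 × √((down + up − 0.10²)/120) = 11.2, 9.6 and 7.8 points at φ = 0.20, 0.41 and 0.61.

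**Rejection rate with no change (60% at both visits).** The unpaired variance is 2pq/n and the true variance is 2pq(1 − φ)/n. In large samples Pearson's test therefore rejects with probability 2·[1 − Φ(1.96/√(1 − φ))].

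| φ | Pearson, formula | Pearson, simulated | McNemar, simulated | Cross-table, simulated |
|---|---|---|---|---|
| 0 | 5.0% | 5.2% | 4.9% | 5% |
| 0.1 | 3.9% | 4.1% | 4.9% | 20% |
| 0.2 | 2.8% | 3.0% | 4.9% | 59% |
| 0.4 | 1.1% | 1.2% | 5.0% | 99% |
| 0.6 | 0.2% | 0.2% | 5.4% | 100% |

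The unpaired test is clearly conservative only once φ is about 0.1 or more.

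**Two worked data sets of 120 patients**

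- Both / down / up / neither = 54 / 18 / 6 / 42, so 60% falls to 50%. Pearson: z = 0.10/√(2 × 0.55 × 0.45/120) = 1.56, p = 0.12. McNemar: z = (18 − 6)/√(18 + 6) = 2.45, p = 0.014. Exact (6 of 24): p = 0.023.
- 60 / 12 / 12 / 36, so no net change. Pearson and McNemar both give p = 1. The cross-table chi-squared is 40.8, p = 2 × 10⁻¹⁰.

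**The case against.** The strongest reply is that McNemar's statistic is itself referred to a chi-squared distribution, so the authors may have used a family name for a paired test. The endpoint is worded as a change from baseline, and the mixed models beside it show that they knew the data were repeated measures. A separate analysis plan, not seen here, may settle the form. This stands as a possibility, and the unpaired reading is an inference. It does not remove the problem: the same section uses the same name for two separate groups, nothing says a paired form is meant, and only one of the candidate tests answers the question properly.

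Other points carry some weight:

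- **Assumed inputs.** φ and the 10-point fall come from no document, and the protocol claims no power here. The figures are an illustration.
- **Number of pairs.** Section 7.3.3 says withdrawn participants will be replaced, so completed pairs could be nearer 150. The pattern is the same: at 150 pairs, Pearson against McNemar is 42% v 49%, 41% v 62% and 39% v 81% at φ = 0.20, 0.41 and 0.61.
- **Confidence interval.** Section 10.2 does not fix the interval method for this endpoint. The interval is too wide only if it is built on the same unpaired basis.
- **Cross-table reading.** It is the less likely reading, and the only one that would produce false positives. It is reported as a secondary risk.

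**Conclusion.** The concern holds. Section 10.2 assigns a chi-squared test to a within-patient change and names no paired form. On the natural reading the test does not fit the design.

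If φ is positive, as is realistic for two liver scans of the same person 6-9 months apart, the consequence is lost power and precision, not excess false positives. Under the assumptions above the power loss runs from none at φ = 0 to 47 percentage points at φ = 0.61 (72% − 25%).

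The reach is limited to one binary component of secondary outcome 3. The primary cT1 comparison, the sample size, the mixed models for continuous PDFF and cT1, and the chi-squared comparison of patients with controls are not part of this point. It should be fixed because a named secondary outcome needs a test that matches its design and the remedy is very cheap.

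**What to change.** In Section 10.2, for this endpoint only, replace the reference to chi-squared tests with McNemar's test, in its exact form if discordant pairs are few, and add the paired difference in proportions with its 95% CI. If McNemar's test was already intended, naming it is enough.

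A logistic GEE or mixed model, with visit as a fixed effect and patient as the cluster, is an acceptable alternative. It would also use patients who have only one scan, but it is not required to resolve the point.

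The cost is one line in a routine protocol amendment, with the approvals described in Section 12.3. No new data or visits are needed.
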